# Proprietary Information of MD Anderson

Protocol # 2016-0251

Date: February 24, 2020

45

the full duration of the trial, or is not in the best interest of the subject to participate, in the opinion of the treating investigator.

34. Has known psychiatric or substance abuse disorders that would interfere with cooperating with the requirements of the trial.

## 5.2 Trial Treatments

The treatment to be used in this trial are outlined in Table 3, Table 4, and Table 5. Please see prescribing information for Zepatier and RBV.

Table 3 Trial Treatments

Drug	Dose/Potency	Dose Frequency	Route of Administration	Regimen/Treatment Period	Use
Pembrolizumab	200 mg	Q3W	IV infusion	Day 1 of each 3-week cycle	Experimental
Zepatier	Tablet: 50 mg elbasvir and 100 mg grazoprevir	qday	PO	Daily See Table 4	Experimental
RBV	Capsule: 200 mg See Table 5	qday	PO	Daily	Experimental

Abbreviations: IV = intravenous; PO = oral; Q3W = every 3 weeks; qday = once daily; RBV = ribavirin.

The duration of Zepatier is dependent upon HCV GTs and presence or absence of resistance polymorphisms. Please see Table 4.

Table 4 Zepatier Trial Treatment Duration With or Without Cirrhosis

Patient Population	Treatment	Duration
GT1a: treatment-naïve without baseline NS5A polymorphisms 	Zepatier	12 weeks
GT1a: Treatment-naïve or PegIFN/RBV-experienced  or with baseline NS5A polymorphisms 	Zepatier + RBV 	16 weeks
GT1b: Treatment-naïve or PegIFN/RBV-experienced 	Zepatier	12 weeks
GT1a  or GT1b: PegIFN/RBV/PI-experienced 	Zepatier + RBV 	12 weeks
GT4: Treatment-Naïve	Zepatier	12 weeks
GT4: PegIFN/RBV-experienced 	Zepatier + RBV 	16 weeks

Abbreviations: GT = genotype; NS5A = non-structural protein 5A; PegIFN = pegylated interferon; RBV = ribavirin.

1. Patients who have failed treatment with PegIFN + RBV.
2. NS5A RAVs at amino acid positions 28, 30, 31, or 93. See Section 2.1 Testing prior to the initiation of therapy, subsection NS5A resistance testing in HCV GT1a-infected patients.
3. For patients with CrCl >50 mL per minute, the recommended dosage of RBV is weight-based (<66 kg = 800 mg per day, 66 to 80 kg = 1000 mg per day, 81 to 105 kg = 1200 mg per day, >105 kg = 1400 mg per day) administered in 2 divided doses with food. For patients with CrCl ≤50 mL per minute, including patients receiving hemodialysis, refer to the RBV tablet prescribing information for the correct RBV dosage.
4. The optimal Zepatier-based treatment regimen and duration of therapy for PegIFN/RBV/PI-experienced GT1a-infected patients with 1 or more baseline NS5A RAVs at positions 28, 30, 31, and 93 has not been established.
5. Patients who have failed treatment with PegIFN + RBV + HCV NS3/4A protease inhibitor (PI): boceprevir, simeprevir, or telaprevir.

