### 4.3.3.2 Zepatier (Grazoprevir and Elbasvir) Dose and Duration

Zepatier is a combination of 2 oral agents. The Zepatier dose regimen is as described in the prescribing information.

A grazoprevir dose of 100 mg qday was selected for Phase 3 trials based on high efficacy and a good safety profile from the Phase 2 dose ranging studies PN003 and PN038, as well as from PN035 and PN039. For detailed information, please refer to the IB.

An elbasvir dose of 50 mg qday was selected for Phase 3 trials based on high efficacy and a good safety profile from a Phase 1b monotherapy study in HCV infected subjects, elbasvir PN002, and a Phase 2a dose ranging study, grazoprevir PN035. For detailed information, please refer to the IB.

Zepatier was approved based upon 2 placebo controlled trials and 4 uncontrolled trials (49-53). The trials were Phase II or Phase III studies of patients with HCV GT1, GT4, and GT6 with compensated liver disease with and without cirrhosis. The names of the trials include C-EDGE, C-Surfer, C-Scape, and C-Salvage. In these studies Zepatier was given for 12 to 18 weeks with and without RBV. Zepatier was administered qday PO in these trials with the doses of 50 mg elbasvir and 100 mg grazoprevir. For subjects who received RBV, the RBV dosage was weight-

based (less than 66 kg = 800 mg per day, 66 to 80 kg = 1000 mg per day, 81 to 105 kg = 1200 mg per day, greater than 105 kg = 1400 mg per day) administered PO in two divided doses with food. Sustained virologic response was the primary endpoint in all trials and was defined as HCV RNA less than the LLOQ at 12 weeks after the cessation of treatment (SVR12).

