### 4.3.3.3 Ribavirin Dose and Duration

The dose and duration of RBV with Zepatier for HCV GT1a: treatment-naïve with baseline NS5A polymorphisms was established in the C-Worthy trial (57,58). See Zepatier prescribing information. For patients with a creatinine clearance (CrCl) greater than 50 mL per minute, the recommended dosage of RBV is weight-based (less than 66 kg = 800 mg per day, 66 to 80 kg = 1000 mg per day, 81 to 105 kg = 1200 mg per day, greater than 105 kg = 1400 mg per day) administered in two divided doses with food. For patients with CrCl less than or equal to 50 mL per minute, including patients receiving hemodialysis, refer to the RBV tablet.

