# Proprietary Information of MD Anderson

Protocol # 2016-0251

Date: February 24, 2020

46

Each Zepatier tablet contains 50 mg elbasvir and 100 mg grazoprevir, is beige, oval-shaped, film-coated, debossed with “770” on one side and plain on the other. The tablets are packaged into a carton (NDC 0006-3074-02) containing two (2) 14-count child-resistant dose packs for a total of 28 tablets.

Store Zepatier in the original blister package until use to protect from moisture. Store Zepatier at 20°C to 25°C (68°F to 77°F); excursions permitted between 15°C to 30°C (between 59°F to 86°F) [see USP Controlled Room Temperature].

In subjects with CrCl greater than 50 mL per minute, RBV will be administered twice a day (BID) PO (in RBV containing arms) at a total daily dose of 800 mg to 1400 mg based on subject weight on Day 1 (Table 5). RBV will be used for 12 to 16 weeks.

Table 5 Recommended Dosing for RBV in Combination Therapy for Subjects with CrCl Greater Than 50 mL Per Minute.

Body Weight in kg (lbs)	RBV Dose	Ribavirin capsules
<66 (<144)	800 mg/day	2 × 200 mg capsules A.M. 2 × 200 mg capsules P.M.
66-80 (145-177)	1000 mg/day	2 × 200 mg capsules A.M. 3 × 200 mg capsules P.M.
81-105 (178-231)	1200/mg day	3 × 200 mg capsules A.M. 3 × 200 mg capsules P.M.
>105 (>231)	1400 mg day	3 × 200 mg capsules A.M. 4 × 200 mg capsules P.M.

Abbreviations: A.M. = ante meridian; P.M. = post meridian; RBV = ribavirin.

Trial Treatment should begin within 3 days of allocation/assignment. However, every effort should be made to begin trial treatment on the day of allocation (ie, Cycle 1 Day 1).

The investigator shall take responsibility for and shall take all steps to maintain appropriate records and ensure appropriate supply, storage, handling, distribution and usage of trial treatments in accordance with the protocol and any applicable laws and regulations.

All trial treatments will be administered on an out-patient basis.

All products indicated in Table 3 will be provided centrally by Merck or locally by the trial site, subsidiary or designee, depending on local country operational or regulatory requirements.

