# Proprietary Information of MD Anderson

Protocol # 2016-0251

Date: February 24, 2020

64

Table 8 Dose Reduction Rules for RBV

Laboratory Parameters	Reduce RBV if	Discontinue Therapy if
HGB without a history of cardiac disease	8.5 to <10 g/dl	< 8.5 g/dl
HGB with a history of stable cardiac disease	<2 g/dL decrease in hemoglobin during any 4-week period during treatment	<8.5 g/dL or <12 g/dL after 4 weeks of dose reduction

Abbreviations: HGB = hemoglobin; RBV = ribavirin

Table 9 Dose Modifications for RBV

Body Weight on Day 1	FDD (mg/day)	1st RBV Reduction		2nd RBV Reduction		3rd RBV Reduction	
		Dose (mg/day)	Number of 200 mg Capsules	Dose (mg/day)	Number of 200 mg Capsules	Dose (mg/day)	Number of 200 mg Capsules
51-65 kg (112-114 lb)	800	600	1 in AM/ 2 in PM	400	1 in AM/ 2 in PM	200	1 in AM/ 2 in PM
66-80 kg (145-177 lb)	1000	800	2 in AM/ 2 in PM	600	1 in AM/ 2 in PM	400	1 in AM/ 2 in PM
81-105 kg (178-231 lb)	1200	1000	2 in AM/ 3 in PM	800	2 in AM/ 2 in PM	600	1 in AM/ 2 in PM
105-125 kg (232-275 lb)	1400	1000	2 in AM/ 3 in PM	800	2 in AM/ 2 in PM	600	1 in AM/ 2 in PM

Abbreviations: AM = ante meridian; FDD = full daily dose; PM = post meridian; RBV = ribavirin

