## 5.2.2 Timing of Dose Administration

Cycle 1 Day 1 treatment with pembrolizumab should begin on the day of allocation, but no later than 3 days from the date the subject is allocated to study treatment. However, every effort should be made to begin trial treatment on the day of allocation.

Trial treatment should be administered on Day 1 of each cycle after all procedures/assessments have been completed as detailed on the Trial Flow Chart (Section 6.0). Trial treatment may be administered up to 3 days before or after the scheduled Day 1 of each cycle due to administrative reasons.

Pembrolizumab 200 mg will be administered as a 30 minute IV infusion Q3W. Sites should make every effort to target infusion timing to be as close to 30 minutes as possible. However, given the variability of infusion pumps from site to site, a window of -5 minutes and +10 minutes is permitted (i.e., infusion time is 30 minutes: -5 min/+10 min).

The Pharmacy Manual contains specific instructions for the preparation of the pembrolizumab infusion fluid and administration of infusion solution.

Pembrolizumab trial treatment will be administered on an outpatient basis.

Subjects will be instructed to take Zepatier orally without regard to food in regimens not requiring RBV. Subjects will be instructed to take Zepatier and RBV (in RBV containing arms) orally, in the morning. RBV should be taken with food. A second daily dose of RBV should be taken by itself, with food, in the evening.

No more than 12 weeks worth of Zepatier/ treatment are to be given and no more than 16 weeks worth of Zepatier/RBV treatment are to be given.

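### Table 3 lists ribavirin as once daily although every other stated frequency (CrCl above 50 mL/min) is twice daily; Tables 5 and 9 also contain band and capsule-count errors (minor)

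*Combined protocol and SAP*

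**What the plan says.** Section 5.2 names Tables 3, 4 and 5 as the outline of trial treatment. In Table 3 the ribavirin row reads "Capsule: 200 mg See Table 5", with qday in the frequency column; the legend gives "qday = once daily; RBV = ribavirin".

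Elsewhere, for creatinine clearance (CrCl) above 50 mL/min:

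- Section 4.3.3.2, describing the Zepatier trials: "administered PO in two divided doses with food".
- Section 4.3.3.3: "administered in two divided doses with food".
- Table 4, footnote 3: "administered in 2 divided doses with food".
- Section 5.2, text leading into Table 5: "RBV will be administered twice a day (BID) PO (in RBV containing arms").
- Table 5: separate A.M. and P.M. capsule counts in every weight band.
- Section 5.2.2: "A second daily dose of RBV should be taken by itself, with food, in the evening".

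Table 5 sets the dose by Day 1 weight, in kg with lb in parentheses: below 66 (below 144), 66-80 (145-177), 81-105 (178-231), above 105 (above 231). Table 9 in Section 5.2.1.5 gives the reduction steps. Its first row is labelled "51-65 kg (112-114 lb"), and its last two rows cover 81-105 kg and 105-125 kg. Nothing states which unit governs or how weight is rounded.

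**The concern.** A treatment table should give one answer. Read alone, Table 3 tells the site to give the whole daily ribavirin dose at once, which contradicts the rest of the protocol. Tables 5 and 9 set and reduce the dose of a drug whose main toxicity, according to Section 5.2.1.5, is hemolytic anemia, with dose steps driven by hemoglobin. Errors in the weight limits or capsule counts could lead to a wrong or disputed dose for an Arm B subject on ribavirin.

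**Working it through.** **Frequency.** Check whether the Table 5 capsule counts, taken as two doses a day, reproduce its daily doses (capsules × 200 mg):

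- below 66 kg: (2 + 2) × 200 = 800 mg
- 66-80 kg: (2 + 3) × 200 = 1000 mg
- 81-105 kg: (3 + 3) × 200 = 1200 mg
- above 105 kg: (3 + 4) × 200 = 1400 mg

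All four match, so Table 5 is a consistent twice-daily schedule and the Table 3 cell is the outlier.

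**Table 5 weight limits.** Conversion: kg = lb ÷ 2.20462, rounded to whole kg because the bands are printed in whole numbers.

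| lb | kg | whole kg | dose by kg | dose by lb |
|---|---|---|---|---|
| 144 | 65.32 | 65 | 800 | none |
| 145 | 65.77 | 66 | 1000 | 1000 |
| 177 | 80.29 | 80 | 1000 | 1000 |
| 178 | 80.74 | 81 | 1200 | 1200 |
| 231 | 104.78 | 105 | 1200 | 1200 |
| 232 | 105.23 | 105 | 1200 | 1400 |

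Across every whole pound from 110 to 279, only 144 and 232 disagree. In the other direction, every whole kilogram from 50 to 126, converted to rounded pounds, gets the same dose in both units.

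**Table 9 weight limits.** 51 kg × 2.20462 = 112.4 lb and 65 kg × 2.20462 = 143.3 lb. The printed upper limit, 114 lb, is 51.7 kg. Since 144 lb rounds to 65 kg and the next row starts at 145 lb, the intended limit is evidently 144. As printed, 115-144 lb is in no pound row. Separately, 105 kg is in both the 1200 mg and the 1400 mg row; Table 5 puts it at 1200 mg. The reduced doses in those two rows are identical (1000, 800 and 600 mg).

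**Table 9 capsule counts.** One capsule in the morning and two in the evening is 3 × 200 = 600 mg. That count is printed correctly against 600 mg, but also against:

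- 51-65 kg, second reduction: 400 mg
- 51-65 kg, third reduction: 200 mg
- 66-80 kg, third reduction: 400 mg

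The other nine of the 12 reduction cells agree with their doses. The 200 mg step is a single capsule and cannot be split into two doses, so Table 9 is not clean evidence for twice-daily dosing and is not counted as such above.

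**The case against.** The strongest reply is that the document resolves all this itself. The Table 3 row sends the reader to Table 5, which shows morning and evening capsules; Table 4 footnote 3 and Section 5.2.2 say the same; and Section 5.2 refers to the ribavirin prescribing information. Kilograms lead in the Table 5 heading and are the only unit in Sections 4.3.3.2 and 4.3.3.3 and in footnote 3, so the pounds are a convenience conversion. In Table 9 the row can be chosen by the full daily dose already assigned. Most of this stands, and it is why the point is minor. It does not make the Table 3 cell right. Nor does choosing the row by full daily dose cure the capsule counts, which are wrong within the row.

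Three stronger readings should be set aside:

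- A reader might infer that every ribavirin instruction specifies two doses a day. It does not: for CrCl of 50 mL/min or less, footnote 3 defers to the prescribing information, and the trial summary and the missed-dose rule in Section 5.2.1.6 give no frequency.
- A reader might infer further dose conflicts at fractions of a kilogram near 66, 80-81 and 105 kg. These require sub-kilogram reading of bands printed in whole numbers, and they vanish once whole kilograms govern.
- A reader might infer that subjects would be under- or over-dosed because of Table 3. The daily total is the same under either frequency.

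**Conclusion.** The Table 3 frequency is wrong as written; the fault is minor. It is one cell in operative dosing text, with the total daily dose unchanged and the correct schedule in the table it points to. The remaining errors are limited: two whole-pound weights in Table 5 (144 lb with no band; 232 lb with a 200 mg/day difference between units), one wrong pound limit and one duplicated kilogram weight in Table 9, and three Table 9 capsule counts 200 or 400 mg/day above the dose beside them.

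This rests on kilograms being the intended unit, which the documents imply but do not state. The 114 lb figure should be checked against the approved document, since a copying error in the text cannot be excluded. Only ribavirin-treated subjects in Arm B (about 15 subjects in all) could be affected. No endpoint, analysis or sample size is touched.

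**What to change.** - Table 3: change the ribavirin frequency to BID, in two divided doses.
- Section 5.2: state that Day 1 weight in kilograms, recorded to the whole kilogram, governs ribavirin dosing.
- Tables 5 and 9: delete the pound values or correct them. If kept, Table 5 becomes below 145, 145-177, 178-232 and above 232 lb (233 ÷ 2.20462 = 105.69, so 106 kg), and the first Table 9 row becomes 112-144 lb. Match the later Table 9 rows to Table 5.
- Table 9: make the last row above 105 kg, so that 105 kg appears once.
- Table 9: replace the three wrong counts with one capsule morning and evening for 400 mg, and a single daily capsule for 200 mg, with the sponsor choosing its time of day.

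The cost is a text amendment to three tables and one sentence; design, visits and analyses do not change.

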# Proprietary Information of MD Anderson

Protocol # 2016-0251

Date: February 24, 2020

46

Each Zepatier tablet contains 50 mg elbasvir and 100 mg grazoprevir, is beige, oval-shaped, film-coated, debossed with “770” on one side and plain on the other. The tablets are packaged into a carton (NDC 0006-3074-02) containing two (2) 14-count child-resistant dose packs for a total of 28 tablets.

Store Zepatier in the original blister package until use to protect from moisture. Store Zepatier at 20°C to 25°C (68°F to 77°F); excursions permitted between 15°C to 30°C (between 59°F to 86°F) [see USP Controlled Room Temperature].

In subjects with CrCl greater than 50 mL per minute, RBV will be administered twice a day (BID) PO (in RBV containing arms) at a total daily dose of 800 mg to 1400 mg based on subject weight on Day 1 (Table 5). RBV will be used for 12 to 16 weeks.

Table 5 Recommended Dosing for RBV in Combination Therapy for Subjects with CrCl Greater Than 50 mL Per Minute.

Body Weight in kg (lbs)	RBV Dose	Ribavirin capsules
<66 (<144)	800 mg/day	2 × 200 mg capsules A.M. 2 × 200 mg capsules P.M.
66-80 (145-177)	1000 mg/day	2 × 200 mg capsules A.M. 3 × 200 mg capsules P.M.
81-105 (178-231)	1200/mg day	3 × 200 mg capsules A.M. 3 × 200 mg capsules P.M.
>105 (>231)	1400 mg day	3 × 200 mg capsules A.M. 4 × 200 mg capsules P.M.

Abbreviations: A.M. = ante meridian; P.M. = post meridian; RBV = ribavirin.

Trial Treatment should begin within 3 days of allocation/assignment. However, every effort should be made to begin trial treatment on the day of allocation (ie, Cycle 1 Day 1).

The investigator shall take responsibility for and shall take all steps to maintain appropriate records and ensure appropriate supply, storage, handling, distribution and usage of trial treatments in accordance with the protocol and any applicable laws and regulations.

All trial treatments will be administered on an out-patient basis.

All products indicated in Table 3 will be provided centrally by Merck or locally by the trial site, subsidiary or designee, depending on local country operational or regulatory requirements.

For any commercially available product that is provided by the trial site, subsidiary, or designee, every attempt will be made to source these supplies from a single lot/batch number. The trial site is responsible for recording the lot number, manufacturer, and expiry date for any locally purchased product as per local guidelines unless otherwise instructed by Merck.

# Proprietary Information of MD Anderson

Protocol # 2016-0251

Date: February 24, 2020

47

## 5.2.1 Dose Selection/Modification

### 5.2.1.1 Dose Selection

The rationale for selection of doses to be used in this trial is provided in Section 4.0 – Background and Rationale.

Details on preparation and administration of pembrolizumab are provided in the Pharmacy Manual.

Details for Zepatier and RBV dosing will be outlined in the prescribing information.

### 5.2.1.2 Dose Modification and Toxicity Management Guidelines for Pembrolizumab

AEs associated with pembrolizumab exposure may represent an immunologic etiology. These immune-related AEs (irAEs) may occur shortly after the first dose or several months after the last dose of pembrolizumab treatment and may affect more than one body system simultaneously. Therefore, early recognition and initiation of treatment is critical to reduce complications. Based on existing clinical study data, most irAEs were reversible and could be managed with interruptions of pembrolizumab, administration of corticosteroids and/or other supportive care. For suspected irAEs, ensure adequate evaluation to confirm etiology or exclude other causes. Additional procedures or tests such as bronchoscopy, endoscopy, skin biopsy may be included as part of the evaluation. Based on the severity of irAEs, withhold or permanently discontinue pembrolizumab and administer corticosteroids. Dose modification and toxicity management guidelines for irAEs associated with pembrolizumab are provided in Table 6.

Table 6 Dose modification and toxicity management guidelines for immune-related AEs associated with pembrolizumab

General instructions:				
irAEs	Toxicity grade or conditions (NCI CTCAE v4.0)	Action taken to pembrolizumab	irAE management with corticosteroid and/or other therapies	Monitor and follow-up
Pneumonitis	Grade 2	Withhold	
 
Administer corticosteroids (initial dose of 1-2 mg/kg prednisone or equivalent) followed by taper
 
	
 
Monitor subjects for signs and symptoms of pneumonitis
 
Evaluate subjects with suspected pneumonitis with radiographic imaging and initiate corticosteroid treatment
 
Add prophylactic antibiotics for opportunistic infections
 

	Grade 3 or 4, or recurrent grade 2	Permanently discontinue		
Diarrhea / colitis	Grade 2 or 3	Withhold	
 
Administer corticosteroids (initial dose of 1-2 mg/kg prednisone or equivalent) followed by taper
 
	
 
Monitor subjects for signs and symptoms of enterocolitis (i.e. diarrhea, abdominal pain, blood or mucus in stool with or without fever) and of bowel perforation (i.e. peritoneal signs and ileus).
 
Subjects with <math>\ge</math>Grade 2 diarrhea suspecting colitis should consider GI consultation and performing endoscopy to rule out colitis.
 
Subjects with diarrhea/colitis should be advised to drink liberal quantities of clear fluids. If sufficient oral fluid intake is not feasible, fluid and electrolytes should be substituted via IV infusion.
 

	Grade 4	Permanently discontinue		

General instructions:				

 
1. Corticosteroid taper should be initiated upon AE improving to Grade 1 or less and continue to taper over at least 4 weeks.
 
2. For situations where pembrolizumab has been withheld, pembrolizumab can be resumed after AE has been reduced to Grade 1 or 0 and corticosteroid has been tapered. Pembrolizumab should be permanently discontinued if AE does not resolve within 12 weeks of last dose or corticosteroids cannot be reduced to <math>\leq 10</math> mg prednisone or equivalent per day within 12 weeks.
 
3. For severe and life-threatening irAEs, IV corticosteroid should be initiated first followed by oral steroid. Other immunosuppressive treatment should be initiated if irAEs cannot be controlled by corticosteroids.
 
				
irAEs	Toxicity grade or conditions (NCI CTCAE v4.0)	Action taken to pembrolizumab	irAE management with corticosteroid and/or other therapies	Monitor and follow-up
Type 1 diabetes mellitus (T1DM) or Hyperglycemia	Newly onset T1DM or Grade 3 or 4 hyperglycemia associated with evidence of $\beta$ -cell failure	Withhold	
 
• Initiate insulin replacement therapy for subjects with T1DM
 
• Administer anti-hyperglycemic in subjects with hyperglycemia
 
	
 
• Monitor subjects for hyperglycemia or other signs and symptoms of diabetes.
 

Hypophysitis	Grade 2	Withhold	
 
• Administer corticosteroids and initiate hormonal replacements as clinically indicated.
 
	
 
• Monitor for signs and symptoms of hypophysitis (including hypopituitarism and adrenal insufficiency)
 

	Grade 3 or 4	Withhold or permanently discontinue1		
Hyperthyroidism	Grade 2	Continue	
 
• Treat with non-selective beta-blockers (e.g. propranolol) or thionamides as appropriate
 
	
 
• Monitor for signs and symptoms of thyroid disorders.
 

	Grade 3 or 4	Withhold or Permanently discontinue1		
Hypothyroidism	Grade 2-4	Continue	
 
• Initiate thyroid replacement hormones (e.g. levothyroxine or liothyroinone) per standard of care
 
	
 
• Monitor for signs and symptoms of thyroid disorders.
 

Nephritis and renal dysfunction	Grade 2	Withhold		
 
• Monitor changes of renal function
 

